9.4.2 ANALYSIS OF THE PRIMARY EFFICACY ENDPOINT(S)

In the models for patient preparedness for discharge (CTM-15 score), data will be included that was provided by the patient or by caregiver (for patients that are not able to answer survey questions). We will use hierarchical linear models (HLM) to compare observations between intervention and usual care periods for CTM-15 score at seven days post-discharge. Linear mixed models or HLM allow for different numbers of patients per site, while accounting for correlated responses between patients within the same SNF. Let Y_{ijk} denote the CTM-15 score for patient k in SNF i and period (enrollment month) j ; ($i = 1, 6$; $j = 1, \dots, 22$). The basic HLM is, where μ is an intercept term, γ_i is a random effect for SNF, accounts for a potential linear temporal trend, δ_j is a random effect for period j nested within SNF i , T_i is an indicator for the treatment condition (i.e., 1 if Connect-Home; 0 is standard discharge procedures), θ is the treatment effect, and ϵ_{ijk} is an error term. Furthermore, we assume a variance components structure such that all random effects are independent with, and where subscripts “c”, “p” and “e” denote cluster (i.e., SNF), period and error variance components, respectively. The correlation structure induced by these random effects allows the within-SNF correlation of outcomes from two patients enrolled in the same month (ICC_W) to be different from the within-SNF correlation of outcomes from patients enrolled in different months (ICC_B). Specifically, by denoting the total variance, the intraclass correlations are $ICC_W = \frac{\sigma_c^2 + \sigma_p^2}{\sigma_c^2 + \sigma_p^2 + \sigma_e^2}$, and $ICC_B = \frac{\sigma_c^2}{\sigma_c^2 + \sigma_p^2 + \sigma_e^2}$. For CTM-15, the basic HLM model will be amended by including additional explanatory variables as fixed effects: CTM-15 score source (patient or caregiver), patient age, gender and race. Due to skewness of the CTM-15 score distribution found in our preliminary data, we expect this outcome will be log-transformed prior to analysis. The group difference in log CTM-15 scores (intervention vs. control) across the study periods will be estimated along with a 95% confidence interval. A sensitivity analysis will be conducted to assess whether the effect of Connect-Home depends on the number of months that an SNF has been operating under the Connect-Home protocol. This is achieved by extending the HLM so that separate effects of Connect-Home are estimated when the Connect-Home protocol has been implemented for ≤ 3 months versus > 3 months in order to examine whether the impact of Connect-Home is sustained three months following its initial implementation in the staff training period. A similar linear mixed model will be applied for the Preparedness for Caregiving outcome, except that respondent source is not included.

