9.2 SAMPLE SIZE DETERMINATION

Computer simulations were used to calculate statistical power for comparing control (standard discharge procedures) and intervention (Connect-Home) conditions for primary outcomes and selected secondary outcomes. For each scenario, 1000 simulated datasets were generated with outcomes clustered within SNFs for the stepped-wedge design in Figure 2 and the respective linear mixed models (Log CTM-15, Preparedness for Caregiving Scale, MQoL-R, Life Space Assessment, Zarit Caregiver Burden scale) and MZIP random intercept model (Days of acute care use). Based on preliminary data for Aim 1, we assumed that the group difference in log CTM-15 scores was $\theta=0.15$. We also assumed that responses from patients within the same SNF in the same period would have an intra-cluster correlation of 0.10 (ICC_w). We assumed that responses from patients or caregivers in the same site but from different periods would have an intra-cluster correlation of 0.05 (ICC_b); together with the total variance of the outcome (SD^2), these values determine and in the linear mixed models of Aims 1 and 2. Under these assumptions and accounting for 23% dropouts, 277 patients at 7 days post-discharge will provide 89% power to detect an increase of 0.15 in the mean log CTM-15 score (equivalent to a 16% increase in

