the mean CTM-15 score) among intervention patients relative to control patients, using a two-sided test at the 5% significance level. Power for Caregiver Preparedness is similarly determined. Power for secondary outcomes at 30 days post-discharge assumes a 30% dropout rate. For the control group in Aim 3, we assumed a prevalence of 22% of patients having at least one day of acute care use and, among those patients, a truncated-at-zero mean of 4.0 days. These assumptions imply that the overall mean number of acute care use days is 0.881 and the excess zero probability is 0.776. For the intervention group, we assumed an overall mean acute care use days of 1.8 and excess zero probability 0.685. Thus, assuming 30% dropout and (optimistically) zero intraclass correlation within SNFs, the MZIP model for independent outcomes has 82% power (not shown); however, the MZIP model with empirical standard errors adjusting for possible clustering within SNFs has 71% power. If there is positive intraclass correlation, power will be lower. However, for days of acute-care use within 60 days of discharge, power is higher than for 30 days due to higher prevalence and mean number of days of acute care use.

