9.4.4 BASELINE DESCRIPTIVE STATISTICS

Co-variate data will be collected about patients in person and from the medical record. Data about caregivers will be collected in person or by phone.

Patient data collected in person:

- Frailty (Study of Osteopathic Fractures Index)⁴⁷
- Social support (ENRICH Social Support Inventory)⁴⁸

Patient data collected with SNF chart abstraction:

- Demographics
- Health insurance status (Medicare Advantage/Medicare fee-for-service/Medicaid/private)

- Living arrangements before index hospitalization
- Medical history (primary diagnosis in the hospital discharge summary, hospital care (critical care, surgery and length of stay)
- Depression (Minimum Data Set section D)⁴⁹
- Function (Minimum Data Set section GG)⁴⁹
- Cognitive status (Minimum Data Set section C)⁴⁹
- SNF care (i.e., SNF length of stay, urgent or acute treatment while in the SNF)⁴⁹
- Discharge destination

Using the problem list in the medical record, the Charlson Comorbidity Index scores will be calculated for each patient.⁵⁰

Patient data collected with Home Health Care chart abstraction:

- Number of days of home health care use in 30 and 60 days after SNF discharge⁴⁰

Caregiver data collected in person or by phone:

- Demographics
- Relationship to patient
- Living arrangements
- Employment
- Count of days per week providing patient care.

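### The primary models pre-specify few prognostic covariates: CTM-15 adjusts only for respondent source and patient age, gender and race, and the caregiver (PCS) model names no caregiver covariate

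*Combined protocol and SAP*

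**What the plan says.** For CTM-15, section 9.4.2 starts from a linear mixed model with treatment, a linear time trend and random effects for SNF and for period within SNF. It then adds four fixed effects: "CTM-15 score source (patient or caregiver), patient age, gender and race". For the caregiver endpoint it says only: "A similar linear mixed model will be applied for the Preparedness for Caregiving outcome, except that respondent source is not included". It does not say whose age, gender and race enter that model.

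Sections 8.1 and 9.4.4 list what is collected. For patients this includes "Frailty (Study of Osteopathic Fractures Index", social support, Minimum Data Set (MDS) depression, function and cognition, and the Charlson index. For caregivers it includes demographics, relationship to the patient, employment and "Count of days per week providing patient care".

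Section 9.4.1 plans supplemental analyses of covariate impact for all three aims. They name insurance provider, SNF length of stay, race and gender, and leave the rest to bivariate analyses. The same section expects covariate balance only if temporal effects are not strong.

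**The concern.** Control and intervention patients are different people, enrolled in different months in only six SNFs. In Figure 2 as extracted, months 1–7 are all control and months 16–22 all intervention, so treatment is closely tied to calendar time. The allocation sets the enrollment dates, so patients are recruited after it, and section 5.4 has them identified through SNF staff. Case mix can therefore differ between conditions. Section 8.1 also records whether SNF admission preceded the COVID-19 research pause, which makes the no-strong-temporal-effects condition less comfortable.

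In this setting, prognostic covariates in the primary model do two useful things: they reduce residual variance, and they adjust for measured case-mix differences along the wedge. They may also make the treatment of missing outcomes more credible. Dropout of 23% is assumed, outcomes are not imputed, and patients hospitalized after discharge are withdrawn (section 7.2), so missingness plausibly depends on severity.

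For PCS, a primary endpoint, the covariate set is open to interpretation. That leaves an avoidable choice to be made after the data are seen.

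**Working it through.** **Inputs from section 9.2.** The test is specified as "using a two-sided test at the 5% significance level". The sample is given as "accounting for 23% dropouts, 277 patients at 7 days post-discharge". The design "will provide 89% power to detect an increase of 0.15 in the mean log CTM-15 score". Patients in the same SNF and period "would have an intra-cluster correlation of 0.10 (ICC_w"; the value for different periods is 0.05. No SD for log CTM-15 is stated.

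**Input from Figure 2 as extracted.** There are 45 control and 47 intervention SNF-months, 92 in all, so 277/92 = 3.01 analyzed patients per SNF-month.

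**Reproducing the plan's figures.** 360 × (1 − 0.23) = 277.2, which agrees with 277. exp(0.15) = 1.162, which agrees with the stated 16% increase. The 89% cannot be confirmed or refuted without an SD. With a linear trend and a normal reference it implies an SD of about 0.194:

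- Power = Φ(0.15/SE − 1.960) = 0.89 requires 0.15/SE = 3.187, so SE = 0.0471.

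**Effect of added covariates.** As fractions of SD², the variance components are 0.05 (SNF), 0.10 − 0.05 = 0.05 (SNF by month) and 0.90 (patient). Suppose the added covariates explain a share R² of the patient-level variance. That component becomes 0.90 × (1 − R²), and the other two are left unchanged. The generalized least squares variance of the treatment effect is then recomputed with intercept, linear month trend and treatment as fixed effects. The SE ratio does not depend on the unknown SD, because all components scale with SD².

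| Assumed R² | SE ratio | Fall in variance (1 − ratio²) | Power from 89% | Power from 80% |
|---|---|---|---|---|
| 5% | 0.982 | 3.5% | 90% | 81% |
| 10% | 0.964 | 7.1% | 91% | 83% |
| 20% | 0.926 | 14.3% | 93% | 86% |

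Example for 10%: 3.187/0.9639 = 3.306; 3.306 − 1.960 = 1.346; Φ(1.346) = 0.911. The last column shows the gain if true power were 80% (SD about 0.221). The variance falls by less than R² because the SNF and SNF-by-month components are held fixed.

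**PCS.** Section 9.2 gives no effect size, SD or power figure for this endpoint, so no gain can be calculated.

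**Timing of the covariates.** In the schedule of activities (section 1.2), the frailty and social support surveys and the caregiver baseline questionnaire sit in the Pre-Discharge column, the same column as Connect-Home Step 1. SNF chart abstraction is marked at day 7 after discharge. The synopsis calls the surveys baseline enrollment surveys, but nothing requires them to be completed before Step 1 begins. For function and cognition an earlier value should exist: section 5.1 uses the MDS mobility score for eligibility and the MDS cognition section to define cognitive impairment. SNF length of stay is known only at discharge and could be changed by the intervention.

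**The case against.** The CTM-15 model is already covariate-adjusted and pre-specified, and it includes a time trend and SNF-level random effects. Which further covariates to add is partly a matter of judgment. A reader might infer that the plan ignores the collected measures altogether. It does not, because section 9.4.1 gives them a supplemental role. That answer is incomplete: most of those covariates are unnamed and selected by screening, race and gender are already in the CTM-15 model, and length of stay is unsuitable as a baseline adjuster.

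A reader might also infer that the PCS model definitely adjusts a caregiver's score for the patient's age, gender and race. That is the literal reading, but the word similar leaves room for another. What is certain is that no caregiver covariate is named.

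Nor is adjustment free. Section 9.4.1 foresees missing covariates, even above 15%, so it cannot be assumed that every participant has every measure. More covariates mean more reliance on its imputation rules. Proxies answer for cognitively impaired patients, so respondent source already carries part of the information in cognition. If the surveys were completed after Step 1 began, adjusting for them could absorb part of the treatment effect. These points stand, and they argue for a short list with dated values rather than against adjustment.

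**Conclusion.** The point holds as one of precision, robustness and pre-specification. The primary CTM-15 model omits clinical prognostic measures that are already collected, and the PCS covariate set is not specified.

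The likely gain for CTM-15 is modest: about 1 to 4 percentage points of power from the stated 89%, if the added covariates explain 5% to 20% of patient-level variance. That R² range is assumed, and the 89% starting point is taken on trust. The benefit for PCS is real in principle but has no number.

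Two stronger conclusions are not supported. No stated figure in the plan is shown to be wrong. And adjustment would reduce measured case-mix differences along the wedge, not remove drift: unmeasured differences and calendar effects that depart from the linear trend would remain.

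**What to change.** In 9.4.2, replace the open wording with a short fixed list for each primary model, for example:

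- **CTM-15:** respondent source, patient age, gender and race, plus frailty, MDS function, Charlson index and social support. Cognition is optional, because respondent source partly captures it.
- **PCS:** caregiver age and gender, relationship to the patient and days of care per week, plus patient function and cognition. State whether patient age, gender and race also stay in.

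State that only values dated at or before enrollment, and before Step 1 starts, are used. For chart data this means the admission MDS values, even though abstraction takes place at day 7. Do not use SNF length of stay as an adjustment covariate, in the supplemental analyses either. Keep the remaining supplemental analyses of 9.4.1 and label them as such.

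The cost is SAP wording, a date check on the surveys, a few degrees of freedom out of about 277 observations, and somewhat more reliance on the missing-covariate rules in 9.4.1. No new data item is needed.

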9.4 STATISTICAL ANALYSES

9.4.1 GENERAL APPROACH

Descriptive statistics will be used for all variables. If patients or caregivers with missing covariates are few (< 5%), unconditional mean imputations will be used to impute missing values for continuous covariates and unconditional mode imputation for categorical covariates. If 5%-15% of patients or caregivers have missing covariates, conditional mean imputation will be used. If missing covariate data exceed 15%, multiple imputation will be used. Missing outcomes will not be imputed. For continuous variables that are highly skewed, the statistical team will log-transform the data for analysis. All statistical tests will be two-tailed with 0.05 significance levels. Also, descriptive statistics will be used to describe intervention fidelity (receipt, delivery and enactment). Finally, in the absence of strong temporal effects, balance in covariates is expected between control and intervention patients; supplemental analyses will involve assessing the impact of the covariates (i.e., insurance provider, SNF length of stay, race, gender, and others determined with bivariate analyses) on outcomes in the statistical models for aims 1-3.

Finally, to determine the extent the intervention effect can be attributed to home health care use, a general multilevel approach will be used to causal mediation analysis to evaluate home health care use as a mediator for intervention effect on outcomes as a secondary analysis. This approach uses two

random effects models within the counterfactual framework: 1) for the mediator (number of days of home health care use) as a function of treatment condition and covariates and 2) for the outcome as a function of treatment condition, mediator, and covariates. Outputs include indirect and direct effects of the intervention.

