The main outcome for Aim 2.3, the number of cumulative days of acute care use, (i.e., days due to re-hospitalizations and emergency department visits), will be modeled using separate marginalized zero-inflated Poisson (MZIP) models with log link. The statistical team will test and estimate the overall effect of Connect-Home relative to standard discharge procedures through exponentiation of the treatment regression coefficient for the overall mean as an incidence rate ratio (IRR) and its 95% confidence interval, basing these on empirical standard errors to allow for possible intraclass correlation within SNFs. MZIP was chosen over the standard ZIP model because although a large number of zero counts (event outcomes) are anticipated, the overall exposure effect of Connect-Home is of interest, and not its effect on an unobserved subpopulation (i.e., latent class). Separate time point-specific generalized linear mixed models (GLMM) with logit link will be used for the binary outcome of whether a resident visited the ED within 30 or 60 days of discharge, respectively, from the SNF. This model type is an extension of ordinary logistic regression that includes random intercepts and period effects for SNFs to account for the within SNF correlation induced by the stepped-wedge design. A similar GLMM will be applied to compare the proportion of hospice referrals between standard discharge procedures and Connect-Home. When events are sparse, SNFs will be treated as fixed effects to mitigate model non-convergence problems.

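### With six SNFs and no small-sample method named, ordinary Wald inference in the primary mixed models would reject a true null at about 7–9.5%, not 5%, at the plan's own ICCs

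*Combined protocol and SAP*

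**What the plan says.** Section 9.4.1 sets the error rate for every analysis: "All statistical tests will be two-tailed with 0.05 significance levels". Section 9.4.2 describes the primary model: a random effect for SNF, a random effect for enrollment month within SNF, a treatment indicator, and a term that "accounts for a potential linear temporal trend". For CTM-15 it adds "additional explanatory variables as fixed effects: CTM-15 score source (patient or caregiver), patient age, gender and race". The stated output is: "The group difference in log CTM-15 scores (intervention vs. control) across the study periods will be estimated along with a 95% confidence interval". PCS gets a similar model without respondent source.

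Sections 9.2 and 9.4.1–9.4.3 name no REML or ML choice, degrees of freedom, reference distribution or small-sample correction for these models. Section 9.2 reports simulated power but no simulated type I error.

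For acute-care days, Section 9.4.3 uses a marginalized zero-inflated Poisson (MZIP) model, "basing these on empirical standard errors to allow for possible intraclass correlation within SNFs". It names neither a small-sample correction nor a reference distribution. Section 9.2 states that "the MZIP model with empirical standard errors adjusting for possible clustering within SNFs has 71% power".

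**The concern.** Six clusters are few for estimating a between-SNF variance. In this design the treatment effect is partly confounded with calendar time, so its standard error depends on that poorly estimated variance. Common choices for a linear mixed model (Wald z, or t on residual degrees of freedom) treat the variance components as if they were well estimated. If they are used, both primary endpoints may be tested above the stated 5% level, with intervals that are too short. The empirical SE for acute-care days raises the same question, because it is built from only six SNF contributions.

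**Working it through.** **Inputs from the documents.** Two-sided 0.05 (9.4.1). Six SNFs on the monthly grid of Figure 2. ICC 0.10 within SNF and month, and 0.05 within SNF across months (9.2). 277 analysed patients, difference 0.15 in log CTM-15, power 89% (9.2). Linear trend, random effects and covariates as in 9.4.2.

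**Step 1: the plan's own figures.** 360 × 0.77 = 277.2 and exp(0.15) = 1.162, so 277 patients and a 16% increase agree. Figure 2 as printed has 92 enrolling SNF-months (45 control, 47 intervention), and 92 × 4 = 368 places against a stated 360. The check keeps 277 analysed.

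With X holding intercept, month and treatment, SE = sqrt{[(X'V⁻¹X)⁻¹] for treatment}. For SNF-month means, in units of SD², V has 0.05 shared within SNF plus 0.05 + 0.90/n on the diagonal, with n = 277/92 = 3.01. This gives SE = 0.2424 × SD; without the month term the same formula gives 0.125 × SD.

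Power = Φ(0.15/SE − 1.96). The plan states no SD, so 89% can only be back-solved: SD = 0.194 gives 0.15/(0.2424 × 0.194) = 3.19 and Φ(3.19 − 1.96) = 0.89. SD 0.25 or 0.30 would give 70% or 54%. The type I error does not depend on SD.

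**Step 2: null rejection at ICCs 0.10/0.05 with the trend.** Data were simulated on the Figure 2 grid, with 277 patients placed at random and normal errors, in two separately coded simulations. Without covariates there were 8,000 and 16,000 runs. With four patient-level covariates of assumed distribution there were 8,000 and 5,134. The Monte Carlo SE is about 0.2–0.4 points.

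| Inference | No covariates | With covariates |
|---|---|---|
| REML, Wald z | 7.3%, 7.2% | 7.7%, 7.5% |
| REML, residual-df t | 7.2%, 7.1% | 7.6%, 7.4% |
| ML, Wald z | 8.5%, 8.7% | 9.5%, 9.2% |
| ML, residual-df t | 8.4%, 8.5% | 9.4%, 9.0% |
| REML, Satterthwaite df only | 6.8%, 6.5% | 7.0% |
| REML, t(5) / t(4) | 2.0% / 1.2% | not run |
| REML, Kenward-Roger | 4.6–5.3%, 5.1% | 4.8–5.4% |

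The Kenward-Roger ranges reflect how variance estimates at zero are handled. With exactly 3 patients per cell and no covariates, REML gives 7.0–7.1% and ML 8.4–8.6%. Coverage runs from 100 − 9.5 = 90.5% to 100 − 7.0 = 93%.

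**Step 3: cause.** The mean REML SE is 0.933 of the true SD of the estimate. Then 1.96 × 0.933 = 1.829 and P(|Z| > 1.829) = 6.7%, so most of the REML excess is an SE that is too small. Residual-df t barely moves the critical value, and Satterthwaite leaves the SE unchanged. Kenward-Roger corrects the SE (ratio 1.000) as well as the df.

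**Step 4: dependence on the ICCs and the trend** (z tests; no covariates unless noted).

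| ICCs | REML | ML |
|---|---|---|
| 0.05/0.025 | 6.8% (7.1% with covariates) | 7.5% (8.3% with covariates) |
| 0.02/0.01 | 5.6% | 6.3% |
| near zero | 4.3% | 4.4% |
| 0.10/0.05, no trend, covariates | 5.1% | 5.3% |

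**Step 5: price of the correction.** With trend and covariates, at an assumed SD of 0.192, power is 88.9% with REML z and 84.8–85.2% with Kenward-Roger. Without covariates, at SD 0.194, it is 88.6% and 84.8%. The median interval is 1.108 times as wide as the REML z interval.

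**Step 6: acute-care days.** Control mean 0.881, excess-zero probability 0.776, intervention mean 1.8 and zero ICC are taken as printed in 9.2, with n = 360 × 0.70 = 252. The model has treatment only and a six-SNF empirical SE; each null rate rests on 20,000 runs.

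| SE and reference | Null rejection | Power |
|---|---|---|
| Uncorrected, z | 13.3% | 88% |
| Uncorrected, t(5) | 6.6% | 73% |
| G/(G−1), t(5) | 5.1% | 67% |
| Kauermann-Carroll, t(5) | 4.8% | 66% |
| Jackknife over SNFs, t(5) | 4.7% | 64% |

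A separate run of all but the Kauermann-Carroll null rates gave 13.0%, 6.5%, 5.0% and 4.6%.

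**The case against.** The strongest reply is that the plan is silent, not wrong. Nothing in it says z or residual-df t will be used. The trial statistician could use Kenward-Roger, or a t with 4 or 5 df, which in the primary model is conservative at 1–2%. The stated 71% power for acute-care days lies near the t(5) result (73%) and far from the normal one (88%), which suggests that the planners had the small number of clusters in mind. That stands. A reader might infer that the primary tests will run at 7–9.5%, or the acute-care test at 13%; the documents support neither. They leave the choice open between tests with quite different error rates.

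The size also depends on the ICCs, and lower values than planned would remove most of the excess. That stands too, though 0.10/0.05 are the plan's own values.

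For PCS, Section 9.2 gives the within-month ICC for patients only. It also says power for caregiver preparedness was determined in a similar way, so similar ICCs are a fair assumption, but PCS was not simulated separately. The model is rebuilt from the verbal description, because the equation is incomplete in the text available, and errors were simulated as normal although the plan expects skewed scores and a log transformation.

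A reader might extend the finding to an MZIP model with a time trend, or to the Poisson and logit mixed models. The plan states no trend for the MZIP model, and the other models were not computed, so no claim is made about them.

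**Conclusion.** The gap is real and matters moderately. Under the planning ICCs and the linear trend, the unstated choice of inference decides whether the CTM-15 test holds 5%. Routine Wald inference adds about 2–2.7 points under REML and 3.4–4.5 under ML. The same applies to PCS if its ICCs are similar. Satterthwaite df alone does not cure it and a cluster-count t over-corrects, so a general intention to allow for few clusters would not settle the matter. The error rates do not depend on the unstated SD; the power cost does.

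For acute-care days, at the plan's zero ICC and without a trend, the excess is about 1.6 points with t(5) and about 8 with z.

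**What to change.** For the CTM-15 and PCS models, prespecify REML with Kenward-Roger adjusted standard errors and degrees of freedom for tests and confidence intervals. Restate CTM-15 power under that test, giving the assumed SD of log CTM-15. The cost is SAP wording and a standard software option, about 4 points of power (about 89% to about 85% at an SD of about 0.19) and an interval about 11% wider. The same wording can cover the linear Aim 2 models, which were not simulated.

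For acute-care days, prespecify a bias-corrected empirical SE, such as G/(G−1) or the leave-one-SNF-out jackknife, with a t(5) reference. Restate the 71% power, which becomes about 64–67% in a no-trend model.
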